**1.0 Objectives**

**A. Objectives**

**A.1. Primary Objective.** To determine the feasibility of conducting a randomized controlled trial (blinded phase) on dexamethasone in cancer patients with dyspnea. Our working hypothesis is that at least 50% of patients will complete the dyspnea numeric rating scale (NRS) on day 7+/-2.

**A.2. Objective #2.** To compare the intensity of dyspnea (NRS), forced expiratory volume (FEV1) and quality of life in cancer patients between baseline and after 4 days of dexamethasone use. Our *working hypothesis* is that 4 days of dexamethasone will improve dyspnea, respiratory function and quality of life for cancer patients.

**A.3. Objective #3.** To compare the intensity of dyspnea (NRS, cancer dyspnea scale), FEV1, and quality of life in cancer patients between baseline and after 7 days of dexamethasone use. Our *working hypothesis* is that 7 days of dexamethasone will improve dyspnea, respiratory function and quality of life for cancer patients.

**A.4. Objective #4.** To compare the intensity of dyspnea (NRS, cancer dyspnea scale), FEV1, in cancer patients between the dexamethasone arm and the placebo arm at 4 and 7 days. Our *working hypothesis* is that dexamethasone will improve dyspnea, and respiratory function for cancer patients compared to placebo.

**A.5. Objective #5.** To compare the intensity of dyspnea (NRS, cancer dyspnea scale), FEV1, and quality of life in cancer patients after 7 days of dexamethasone between the dexamethasone arm (8mg BID for 4 days followed by 4mg BID for 3 days) and the placebo arm (4mg BID for 7 days during the open label phase). Our *working hypothesis* is that a higher dose of dexamethasone will improve dyspnea, respiratory function and quality of life for cancer patients compared the lower dose.

**2.0 Background and Significance**

**B. Background and Significance**

[figure not shown]
**B.1. Significance of Dyspnea.** Dyspnea is a subjective awareness of difficulty breathing, which may be associated with the distressing sensation of suffocation. It is one of the most common and most feared symptoms among cancer patients, occurring in approximately 20-40% of patients at the time of diagnosis of advanced disease (Ripamonti *et al.* 1998, Tishelman *et al.* 2007) and in up to 70% of patients in the last 6 weeks of life (Ben-Aharon *et al.* 2008). Dyspnea is associated with fatigue, anxiety, decreased function and lower quality of life. Furthermore, dyspnea has been shown to be an important prognostic factor in patients with advanced cancer (Hauser *et al.* 2006, Maltoni *et al.* 2005).

**B.2. The Pathophysiology of Dyspnea** is shown in Figure 1. The sensory cortex receives afferent input from mechanoreceptors in airways and the chest wall, stretch and irritant receptors in the lungs, chemoreceptors in the brainstem, and other signals from the motor cortex, generating the sensation of breathlessness (Mahler 2011, Manning and Schwartzstein 1995). Causes of dyspnea can be classified as cancer-related, treatment-related and/or psychological factors. Progressive disease may result in parenchymal metastasis, lymphangitic carcinomatosis, airway obstruction, atelectasis, and/or pleural effusion, all of which may cause difficulty breathing.

**B.3. The Current Management of Dyspnea** involves treatment of any reversible causes and supportive measures to minimize the sensation of dyspnea. Relief of dyspnea can be achieved through a number of pharmacologic and non-pharmacologic measures. Common medications for dyspnea include opioids, bronchodilators, corticosteroids and benzodiazepines (Ben-Aharon *et al.* 2008, Cranston *et al.* 2008, Jennings *et al.* 2002). A systemic review suggested that oral and parenteral, but not nebulized, opioids are effective in managing dyspnea (Jennings *et al.* 2002). However, the potential benefit of opioids is limited by their adverse effects, including sedation and opioid-induced neurotoxicity at higher doses. Supplemental oxygen has been shown to be efficacious only in patients with hypoxemia (Abernethy *et al.* 2010, Cranston *et al.* 2008). For patients with chronic obstructive pulmonary diseases, systemic corticosteroids have been clearly shown to reduce respiratory symptoms, improve FEV1 and shorten hospitalization in acute exacerbations (Falk *et al.* 2008, Walters *et al.* 2009, Wood-Baker *et al.* 2007). Furthermore, inhaled steroids have been demonstrated to improve various clinical outcomes in COPD patients including the number of physician visits and airway hyperreactivity (Calverley *et al.* 2007, Lung Health Study Research 2000, Yang *et al.* 2007). However, the efficacy of corticosteroids for dyspnea has not been clearly elucidated in cancer patients.

**B.4. Corticosteroids for Dyspnea in Cancer Patients.** No study to date has specifically examined the relationship between inflammation and dyspnea in cancer patients. However, cancer is known to induce host inflammatory response and often produces a number of cytokines with both systemic and peripheral effects (Wang *et al.* 2010). Thus, cancer is similar to COPD which is also a disease characterized by a significantly inflammatory component, including airway wall infiltration of T lymphocytes and macrophages, increased lung TNF $\alpha$  and IL8, increased lung IL6 during exacerbations, and elevated serum leptin, IL6, TNF $\alpha$ , CRP, fibrinogen, peripheral neutrophil activation, and activation of apoptosis of peripheral lymphocytes (Falk *et al.* 2008). The severity of dyspnea of COPD as determined by the FEV1 correlated with concentrations of IL-1b, MIP-1b, CD83, IL-1 receptor 2, and IL-1 receptor antagonist as measured by gene microarray (Oudijk *et al.* 2005). Steroids have been shown to modulate the inflammatory response and improve dyspnea (Calverley *et al.* 2003, Lapperre *et al.* 2009). More recently, a randomized controlled trial on an IL8 monoclonal antibody also found significant improvement in the sensation of dyspnea (Mahler *et al.* 2004). The available evidence suggests that modulation of the inflammatory response may improve the sensation of dyspnea. Given that inflammation is a significant mediator of dyspnea in cancer patients, we hypothesize that corticosteroids could have a therapeutic benefit for cancer patients.

Few clinical studies have addressed the role of corticosteroids for dyspnea in cancer patients. In a case series, Elsayem *et al.* reported significant improvement in dyspnea after administration of high dose steroids among patients with upper airway obstruction (Elsayem and Bruera 2007). In a prospective series, Hardy *et al.* found that 5/13 advanced cancer patients experienced some improvement with dexamethasone, 6/13 had no change and 2/13 did worse (Hardy *et al.* 2001). Matso *et al.* surveyed 120 Japanese palliative care physicians about their use of steroids. 37% of physicians perceived the positive effect of steroids on dyspnea to take place within 24 hours, 38% within 1-2 days, and 24% within 3-7 days (Matsuo *et al.* 2011). The main perceived predictors of steroid efficacy were lymphangitic carcinomatosis, airway obstruction, multiple lung metastases. The main side effects after 1 week of use were hyperglycemia, insomnia, delirium and oral candidiasis. A recent systematic review on dyspnea interventions found no study on corticosteroids, and concluded that high quality randomized controlled trials are needed to examine the effectiveness of corticosteroids for dyspnea (Viola *et al.* 2008). A study examined the effect of prednisone in healthy men on induced dyspnea using inspiratory resistors and breathholding, and concluded that prednisone intake was associated with significant increase in minute ventilation during breathing compared to placebo (Kallas De Carvalho *et al.* 2002).

[figure not shown]
**Figure 1. Conceptual Framework for Dyspnea and Potential Mechanisms of Action of Corticosteroids.**

**B.5. Preliminary data.** One of our co-investigators, [name], recently completed a randomized controlled trial comparing dexamethasone 4mg twice a day versus placebo for cancer related fatigue, with dyspnea as a secondary endpoint. Use of dexamethasone was associated with significant improvement in dyspnea compared to placebo.

	Dexamethasone Arm		Placebo Arm		P-value
	N	Change	N	Change	
Day 4 - baseline	49	-2 (-4 to 0)	44	-1 (-3 to 0)	0.31
Day 8 - baseline	43	-1 (-3 to 1)	38	0 (-2.25 to 0)	0.59
Day 15 - baseline	36	-2 (-4.75 to 0)	32	0 (-2.75 to 0)	0.04
Day 22 - baseline	35	-2 (-4 to 0)	26	0 (-3 to 1)	0.04

### 3.0 Experimental Approach

**C.1. Overall Study design.** This is a 2-arm, double blind, parallel randomized controlled trial of dexamethasone and placebo for cancer patients with dyspnea (Figure 1). The main goal of this study is to determine the effect size for both dexamethasone and placebo arm to inform a larger, adequately powered confirmatory randomized controlled trial. For this preliminary study, we plan to enroll 20 patients per arm, with a total of 40 patients for the entire study (see statistical considerations for more details). Patients will be randomized to either dexamethasone or placebo for 7 days in a blinded fashion; this will be followed by an open label phase in which patients in both arms would take dexamethasone for 7 days. The rationale for the open label phase is to give all patients an opportunity to try the study medication, and to examine the use of dexamethasone at a different dose as an exploratory endpoint (objective #5). Based on our experience conducting symptom control trials, we believe this study design is feasible and would not add undue burden for patients. To reimburse patients for their time and effort, we will provide a gift card for \$20 per visit (day 7+/-2 and day 14+/-2).

**C.2. Eligibility Criteria.** The eligibility criteria are shown in Table 2.

Table 2. Study Eligibility Criteria

Inclusion Criteria
 
 
Diagnosis of cancer
 
Dyspnea with an average intensity level >3/10 on the numeric rating scale over the past week
 
Clinical or radiologic history of lung/pleural involvement (primary or metastatic), lymphangitic carcinomatosis or airway involvement secondary to tumor infiltration
 
Outpatients at MD Anderson Cancer Center seen by the Supportive Care, Rehabilitation Service, Thoracic Oncology or Pulmonary Medicine
 
Able to communicate in English
 
Karnofsky performance status <math>\geq 40\%</math>
 
Age 18 or older
 
Permission from the attending medical oncologist if the patient is currently on an interventional cancer therapy trial.
 
 
Exclusion Criteria
 
 
Delirium (i.e. Memorial delirium rating scale >13)
 
Oxygen saturation <90% despite supplemental oxygen >6L/min
 
Previous allergic reactions to dexamethasone
 
Uncontrolled hyperglycemia as defined by any blood glucose of >300 mg/dl in the past two weeks
 
Severe anemia (Hb <7g/L) not corrected prior to study enrollment (bloodwork is not required if patient did not have recent chemotherapy within last 2 weeks)
 
Post-surgical open wound that has not been healed at the time of enrollment
 
Any infection requiring antibiotics within the past 2 weeks
 
Major surgery within the past 2 weeks
 
Megestrol use at the time of study enrollment
 
Neutropenia (absolute neutrophil count < 1.0) (bloodwork is not required if patient did not have recent chemotherapy within last 2 weeks)
 
Currently on or expected to start cytotoxic chemotherapy within 1 week of study enrollment
 
Chronic obstructive pulmonary disease (COPD) exacerbation at the time of study enrollment
 
Heart failure exacerbation at the time of study enrollment
 
Chronic systemic corticosteroid use (>14 days) at the time of study enrollment
 
Unwilling to provide informed consent
 

**C.3. Study screening.** A 2 step consent process will be used. A verbal script is provided in the Appendix P. First, a verbal consent will be obtained by the study staff to proceed with screening of potential participants for eligibility and to characterize their dyspnea using the dyspnea survey and the cancer dyspnea scale. Eligible patients will then be formally enrolled onto the study after they have signed the informed consent indicating a willingness to participate in the trial. The number of patients screened, approached, eligible and enrolled will be documented. Reasons for refusal for eligible patients will also be captured.

**C.4. Randomization.** A computer generated sequence in permuted blocks will be used to assign patients to either dexamethasone or placebo via CORE, a secured website. We will stratify by FEV1/FVC ratio (<0.8 vs.  $\geq 0.8$ ). CORE will set up a Randomization website and Investigational Pharmacy personnel will perform the randomization assignment. [name], our research manager, will provide the necessary CORE training for the research team.

**C.5. Blinding.** Both patients and the research staff conducting the assessment will be blinded to the treatment assignment. Placebo capsules identical to dexamethasone 4mg capsules in appearance and taste will be compounded by Green Park Compounding Pharmacy, and both will be dispensed by Investigational Pharmacy at MD Anderson. At the end of the blinded phase, we will assess blinding by asking patients which study arm they believe they have been randomized to.

**C.6. Research staff.** An orientation will be held with research staff involved in this study to introduce them with the study design, and standardize the provision of each intervention.

**C.7. Study Interventions.** The intervention arm will receive dexamethasone 8 mg (2 capsules of 4 mg) given orally twice a day for 4 days, then 4 mg given orally twice a day for 3 days. This dose was chosen partly based on our feasibility data demonstrating that dexamethasone improved dyspnea.

Dexamethasone is a commonly used medication in cancer patients. It is approved by the US Food and Drug Administration for treatment of multiple indications, including allergic disorder (including asthma), cerebral edema associated with primary or metastatic brain tumor, craniotomy, or head injury, collagen disease, disorder of ear, disorder of endocrine system, disorder of eye, disorder of gastrointestinal tract, disorder of hematopoietic structure, disorder of respiratory system (treatment of berylliosis, fulminating or disseminated pulmonary tuberculosis (when used concurrently with appropriate antituberculosis therapy), idiopathic eosinophilic pneumonias and symptomatic sarcoidosis, Loeffler's syndrome not manageable by other means and aspiration pneumonitis), disorder of skin, exacerbation of multiple sclerosis, hypercalcemia of malignancy, idiopathic thrombocytopenic purpura, inflammatory disorder of musculoskeletal system, macular retinal edema, mycosis fungoides, neoplastic disease, palliative management of leukemias and

lymphomas, nephrotic syndrome, Idiopathic or due to lupus erythematosus without uremia, non-infectious posterior uveitis, trichinosis with neurologic or myocardial involvement, tuberculosis of meninges with subarachnoid block or impending block when used concurrently with antituberculosis therapy

([http://www.thomsonhc.com/micromedex2/librarian/ND\\_T/evidenceexpert/ND\\_PR/evidenceexpert/CS/7CB60A/ND\\_AppProduct/evidenceexpert/DUPLICATIONSHIELDSYNC/0CC381/ND\\_PG/evidenceexpert/ND\\_B/evidenceexpert/ND\\_P/evidenceexpert/PFActionId/evidenceexpert.DisplayDrugdexDocument?docId=0221&contentSetId=31&title=Dexamethasone&servicesTitle=Dexamethasone&topicId=clinicalApplicationsSection&subtopicId=therapeuticUsesSection#4.5.A.74](http://www.thomsonhc.com/micromedex2/librarian/ND_T/evidenceexpert/ND_PR/evidenceexpert/CS/7CB60A/ND_AppProduct/evidenceexpert/DUPLICATIONSHIELDSYNC/0CC381/ND_PG/evidenceexpert/ND_B/evidenceexpert/ND_P/evidenceexpert/PFActionId/evidenceexpert.DisplayDrugdexDocument?docId=0221&contentSetId=31&title=Dexamethasone&servicesTitle=Dexamethasone&topicId=clinicalApplicationsSection&subtopicId=therapeuticUsesSection#4.5.A.74)). However, it has not been specifically approved for management of dyspnea.

Dexamethasone is commonly used in oncology practice for management of cerebral edema, spinal cord compression, chemotherapy induced nausea and vomiting, bowel obstruction, pain, anorexia, dyspnea and fatigue. For patients with chronic obstructive pulmonary diseases, systemic corticosteroids have been clearly shown to reduce respiratory symptoms, improve FEV1 and shorten hospitalization in acute exacerbations (Falk et al. 2008, Walters et al. 2009, Wood-Baker et al. 2007). Furthermore, inhaled steroids have been demonstrated to improve various clinical outcomes in COPD patients including the number of physician visits and airway hyperreactivity (Calverley et al. 2007, Lung Health Study Research 2000, Yang et al. 2007). However, the efficacy of corticosteroids for dyspnea has not been clearly elucidated in cancer patients.

Our study proposes to use oral dexamethasone for the management of dyspnea. The dose of dexamethasone we plan to use is 8mg PO BID for 4 days, then 4 mg PO BID x10 more days. This is similar to doses we use for CINV prophylaxis (8-20mg IV/PO prior to chemotherapy, then 4-8mg q12h for up to 4 days after chemotherapy) (Mullin and Beckwith, [www.ifvrh.com/policies\\_quick\\_ref/Treatment\\_of\\_CINV.html](http://www.ifvrh.com/policies_quick_ref/Treatment_of_CINV.html)). This study is purely exploratory in nature, and we do not plan to seek FDA approval for the new indication of dyspnea.

The control arm will receive placebo capsules prepared by a compounding pharmacy (Green Park Compounding Pharmacy) identical in appearance to dexamethasone 4 mg capsules, and will be instructed to take two capsules twice a day for 4 days, followed by one capsule twice a day for 3 days.

In the open label phase, patients assigned to either arm will be asked to take dexamethasone 4 mg orally twice a day for 7 days. Both dexamethasone and placebo capsules used throughout this study will be compounded by Green Park Compounding Pharmacy and dispensed by Investigational Pharmacy at MD Anderson. Dexamethasone/placebo capsules will be provided free of charge to patients during the 14 day study period.

**C.8. Medication use during study.** We will ask patients to record the use of study medications using a medication diary. We will also keep track of their adherence by asking them to bring their medication boxes for a pill count. Phone call reminders will be provided daily. To document the co-intervention effect on dyspnea, patient use of regular and breakthrough opioids (for any reason) and bronchodilators at enrollment and during the study. Patients will receive daily phone calls for reminders and assessments. They can take it as soon as possible if they forget a dose.

**C.9. Feasibility endpoints.** Our primary objective is to test the feasibility of a protocol that uses dexamethasone and placebo for dyspnea, and to determine the feasibility of these two interventions for advanced cancer patients with persistent dyspnea. We will document the following:

- Rates of recruitment and retention (see section D1).
- Reasons for refusal and dropout
- Outcome measure—we will compare the sensitivity of Numeric rating scale and Borg scale to change, and identify key measure for future study
- Participant satisfaction—participants will provide an opinion regarding their satisfaction with study overall

**C.10. Study assessments.** See Table 4 for a detailed description of all study assessments.

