## 4.0 Statistical Analysis

**D.1. Sample Size Calculation.** This pilot study is based on a convenience sample of 20 subjects per arm.

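### Table 2 sets the severe anemia exclusion at a hemoglobin below 7 g/L (0.7 g/dL); number and unit do not fit the label and should be reconciled

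*Combined protocol and SAP*

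**What the plan says.** The eligibility criteria are in section 3.0, C.2, Table 2. One exclusion opens with "Severe anemia (Hb", then a less-than sign, and continues "7g/L) not corrected prior to study enrollment". A bracket in the same line adds that "bloodwork is not required if patient did not have recent chemotherapy within last 2 weeks".

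The population to which this applies is set by the inclusion criteria in the same table: "Outpatients at MD Anderson Cancer Center seen by the Supportive Care, Rehabilitation Service, Thoracic Oncology or Pulmonary Medicine", with a "Karnofsky performance status" of at least 40%.

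No other part of the document gives a hemoglobin limit or a hemoglobin unit. The assessment schedule (Table 4) does not list a hemoglobin measurement.

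**The concern.** The line has two parts that should agree: a label (severe anemia) and a definition (a number with a unit). They do not. The definition describes a hemoglobin far below anything one would expect in a person attending an outpatient clinic, so it cannot be what the label means.

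This is operative text, not background. It is the rule a screener applies before a patient is enrolled and randomized. A screener who follows the definition and one who follows the label can reach opposite decisions on the same patient. C.3 also requires the number of eligible patients to be recorded, and that count depends on which reading is used.

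**Working it through.** The plan derives no figure here, so there is nothing to reproduce. The check is a unit conversion, followed by a comparison of the two readings.

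**Inputs**

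- Limit as printed: hemoglobin below 7 g/L (Table 2, exclusion criteria).
- Label: severe anemia (same line).
- Population: outpatients with Karnofsky status of at least 40% (Table 2, inclusion criteria).
- Testing rule: bloodwork waived without chemotherapy in the last 2 weeks (same line as the limit).
- Conversion: 1 L = 10 dL, so 1 g/dL = 10 g/L.

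**Conversion**

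- Limit as printed, in g/dL: 7 / 10 = 0.7 g/dL.
- Same number with the unit g/dL, in g/L: 7 × 10 = 70 g/L.
- Ratio of the two: 70 / 7 = 10.

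**Where the two readings disagree.** Let h be a patient's known, uncorrected hemoglobin in g/dL.

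- h below 0.7: excluded on either reading.
- h from 0.7 up to, but not including, 7: admitted on the printed unit, excluded if the same number is read in g/dL.
- h of 7 or more: admitted on either reading.

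The unit therefore matters only in the middle band. The g/dL reading is used here only to show the size of the discrepancy; the document does not say which limit was intended.

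**Who can be affected.** The criterion can act only where a hemoglobin value exists. Under the waiver, that means patients with chemotherapy in the last 2 weeks, plus any others whose hemoglobin happens to be known. Table 2 separately excludes patients currently on cytotoxic chemotherapy or expected to start it within 1 week, which narrows the first group further. The document gives no hemoglobin distribution, so the number of patients in the middle band cannot be calculated.

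**Link to the statistics.** Section 4.0, D.1 states: "This pilot study is based on a convenience sample of 20 subjects per arm". The primary outcome in D.2 is completion of the dyspnea numeric rating scale at day 7 +/- 2, with feasibility declared at 20 or more successes. Neither uses hemoglobin. The t-tests planned for Objectives 2 to 5 do not use it either.

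**The case against.** The strongest reply is that the slip corrects itself in use. The line is headed severe anemia, the printed limit is implausible on its face, and trained staff at one centre would see that. Much of this stands: the error is certain in the text, but its effect on screening is not. It does not make the text right, because a numeric eligibility limit should not depend on staff setting it aside.

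A second reply is that the letter d may have been lost when the PDF was read. Section 4.0, D.2 has a comparable oddity, where the day 7 +/- 2 window appears once as day 72. The possibility cannot be excluded, but nothing shows it, and the per-decilitre unit of the glucose criterion ("300 mg/dl in the past two weeks") survives in the same table. It lowers confidence only a little. The glucose unit is not evidence of an error in itself: two analytes may properly be reported in different units.

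A reader might also infer more than the document supports:

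- *That the exclusion removes nobody and severely anemic patients will be randomized.* This needs a hemoglobin distribution and literal screening. The document gives no such distribution and does not show how staff will read the line.
- *That each such patient is a stated share of an arm.* One patient out of 20 is simple division and says nothing about how many would be wrongly enrolled, which could be none.
- *That this is a failed safety rule or will cause audit findings.* The document does not call the criterion a safety exclusion and says nothing about audit.
- *That correcting anemia during the blinded phase would bias the results.* The document does not name anemia as a cause of dyspnea; the examples in B.2 do not include it. In the between-arm comparison (Objective 4), randomization would balance such corrections in expectation. The within-arm paired tests could in principle be affected, but by an amount that cannot be quantified.

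**Conclusion.** The point holds as a minor correction. The severe anemia exclusion is wrong as written: the printed limit equals 0.7 g/dL, a factor of ten below the same number in g/dL, and number and unit do not fit the label. Read literally, an outpatient with realistic severe anemia and a known hemoglobin would not meet it.

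The conversion is exact. The statement about literal reading rests on one assumption from outside the document: that a hemoglobin below 0.7 g/dL would not be seen in an outpatient with a Karnofsky status of at least 40%. The slip is probably typographical. Its practical effect is unknown in size and is limited by the bloodwork waiver. It gives no reason to change the sample size, the primary endpoint or the planned analyses.

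**What to change.** The sponsor should reconcile the number, the unit and the label in this line of Table 2, stating the limit in the unit the site laboratory reports and with the investigator's confirmation. Screening forms that repeat the limit, if there are any, should be brought into line. The choice of limit is a clinical matter, and none is proposed here. The cost is a one-line protocol correction; nothing in section 4.0 needs to be rewritten.
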